Grade 4	Discontinue Study drug/study regimen.	Treat accordingly as per institutional standard	
	Note for grade 4 laboratory abnormalities, decision to discontinue would be based on accompanying clinical signs/symptoms and as per treating investigator's clinical judgment and in consultation with the Overall PI.		

Abbreviations:

AChE = acetylcholine esterase; ADA = American Dietetic Association; AE = adverse event; ALP = alkaline phosphatase; ALT = alanine aminotransferase; AST = aspartate aminotransferase; CT = computed tomography; GI = gastrointestinal; IDS=Infectious Disease Service; ILD = interstitial lung disease; IM = intramuscular; irAE = immune-related adverse event; IV = intravenous; NCI CTCAE = National Cancer Institute Common Terminology Criteria for Adverse Events; PO = by mouth; TNF = tumor necrosis factor; TSH = thyroid stimulating hormone; ULN = upper limit of normal.

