5. TREATMENT PLAN

5.1 Treatment Regimen

One cycle is defined as 28 consecutive days. Participants will receive durvalumab and tremelimumab both via IV infusion on day 1 of each cycle. Participants will receive tremelimumab for up to 4 cycles (4 doses). Beginning with cycle 5 day 1, participants will continue to receive durvalumab alone (as monotherapy).

Treatment will be administered on an outpatient basis. Reported adverse events and potential risks are described in **Section 7**. Appropriate dose modifications are described in **Section 6**. No investigational or commercial agents or therapies other than those described below may be administered with the intent to treat the participant's malignancy, with the exception of palliative

radiation therapy or surgical resection to non-target lesions. Bisphosphonate use is permitted.

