5.5.2 Excluded Concomitant Medications

The following medications are considered exclusionary during the study:

- 1. Any investigational anticancer therapy other than the protocol specified therapies
- 2. Any concurrent chemotherapy, radiotherapy (except palliative radiotherapy), immunotherapy, biologic, or hormonal therapy for cancer treatment, other than any stated protocol specified therapies. Concurrent use of hormones for noncancer-related conditions (e.g., insulin for diabetes and hormone replacement therapy) is acceptable. Local treatment of isolated lesions for palliative intent is acceptable (e.g., by local surgery or radiotherapy). Bisphosphonate use is permitted.
- Immunosuppressive medications including, but not limited to systemic corticosteroids at doses exceeding 10 mg per day, methotrexate, azathioprine, and TNF-α blockers. Use of immunosuppressive medications for the management of investigational product-related AEs or in subjects with contrast allergies is acceptable. In addition, use of inhaled, topical, ophthalmic, and intranasal corticosteroids is permitted, along with local steroid injections.
- 4. Live attenuated vaccines within 30 days of durvalumab and tremelimumab dosing (i.e., 30 days prior to the first dose, during treatment with durvalumab and tremelimumab, and for 30 days post discontinuation of durvalumab and tremelimumab). Inactivated vaccines, such as the injectable influenza vaccine, are permitted.

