Toxicity	Grade of the Event (NCI CTCAE version 4.03)	Dose Modifications	Toxicity Management
			If no improvement within 5 days of IV methylprednisolone 2 to 4mg/kg/day or equivalent, promptly start further immunosuppressives (e.g. infliximab at 5mg/kg once every 2 weeks). Caution: Rule out bowel perforation and refer to infliximab label for general guidance before using infliximab.
			Once improving, gradually taper steroids over ≥28 days and consider prophylactic antibiotics, antifungals, and anti PCP treatment (please refer to current NCCN guidelines for treatment of cancer-related infections [Category 2B recommendation]) ⁴⁵ .
Hepatitis (Elevated AST [SGOT], ALT [SGPT], and/or total bilirubin)	Grade 1	No dose delay required. If it worsens, treat as Grade 2 event.	Monitor and evaluate liver function tests: AST, ALT, alkaline phosphatase (ALP) and total bilirubin as per protocol.
Note: Infliximab should not be used for management of Immune Related			Evaluate for alternative etiologies (e.g., viral hepatitis, disease progression, concomitant medications).
Hepatitis	Grade 2	Hold study drug/study regimen dose.	Regular and frequent checking of LFTs (e.g. every 1-2 days) until elevations are improving or resolved.
		 If toxicity worsens then treat as Grade 3 or Grade 4 If improves to baseline then treat at next 	If no resolution to \leq Grade 1 or baseline in 2 days, discuss with the Overall PI.

Table 3: Do	sing Modifi	cation and Toxicity Manage mediated Adverse R	ement Guidelines for Specific Immune- Reactions
Toxicity	Grade of the Event (NCI CTCAE version 4.03)	Dose Modifications	Toxicity Management

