		scheduled treatment date. Study drug/study regimen can be resumed at the next scheduled dose once event stabilizes to grade ≤1 or baseline and at least 5 days have passed after completion of steroid taper.	If event is persistent (>5 days) or worsens, promptly start prednisone 1- 2mg/kg/day or IV equivalent. If still no improvement within 5 days despite 1-2mg/kg/day of prednisone or IV equivalent, consider additional workup and prompt treatment with IV methylprednisolone 2-4mg/kg/day or equivalent. If still no improvement within 5 days despite 2-4mg/kg/day of IV methylprednisolone or equivalent, promptly start immunosuppressives (mycophenolate mofetil ¹ or equivalent). Infliximab should NOT be used. Once improving, gradually taper steroids over ≥28 days and consider prophylactic antibiotics, antifungals and anti PCP treatment (please refer to current NCCN guidelines for treatment of cancer-related infections [Category 2B recommendation]) ⁴⁵ .
	Grade 3	For elevations in transaminases $\leq 8 \times$ ULN, or elevations in bilirubin $\leq 5 \times$ ULN:	Promptly initiate empiric IV methylprednisolone at 1 to 4 mg/kg/day or equivalent.
		Hold study drug/study regimen	If still no improvement within 5 days despite 1 to 4 mg/kg/day methylprednisolone IV or equivalent,

Table 3: Dos	ing Modifie	cation and Toxicity Manag mediated Adverse F	ement Guidelines for Specific Immune- Reactions
Toxicity	Grade of the Event (NCI CTCAE version 4.03)	Dose Modifications	Toxicity Management

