		dose until resolution to \leq Grade 1 or baseline • Resume study drug/study regimen administration at the next scheduled dose if elevations downgrade \leq Grade 1 or baseline within 14 days Permanently discontinue study drug/study regimen if the elevations do not downgrade to \leq Grade 1 or baseline within 14 days. For elevations in transaminases > 8 × ULN or elevations in bilirubin > 5 × ULN, discontinue study drug/study regimen. Permanently discontinue study drug/study regimen for any case meeting Hy's law criteria (ALT > 3x ULN + bilirubin > 2x ULN without initial findings of cholestasis [i.e. elevated alkaline PO4] and in the absence of any alternative cause ⁴⁶).	promptly start treatment with immunosuppressive therapy (mycophenolate mofetil or equivalent). Infliximab should NOT be used. Consider hepatology consult, abdominal work-up, and imaging as appropriate. Once improving, gradually taper steroids over ≥28 days and consider prophylactic antibiotics, antifungals and anti PCP treatment (please refer to current NCCN guidelines for treatment of cancer-related infections [Category 2B recommendation]) ⁴⁵ .

Table 3: Dos	sing Modifi	ing Modification and Toxicity Management Guidelines for Specific Immune mediated Adverse Reactions		
Toxicity	Grade of the Event (NCI CTCAE version 4.03)	Dose Modifications	Toxicity Management	
	Grade 4	Permanently discontinue study drug/study regimen.	Promptly initiate empiric IV methylprednisolone at 1 to 4 mg/kg/day or equivalent.	
			If still no improvement within 5 days despite 1 to 4 mg/kg/day methylprednisolone IV or equivalent, promptly start treatment with immunosuppressive therapy (mycophenolate mofetil or equivalent). Infliximab should NOT be used.	
			Consider hepatology consult, abdominal work-up, and imaging as appropriate.	
			Once improving, gradually taper steroids over ≥28 days and consider prophylactic antibiotics, antifungals and anti PCP treatment (please refer to current NCCN guidelines for treatment of cancer-related infections [Category 2B recommendation]) ⁴⁵ .	
Nephritis or Renal Dysfunction (Elevated		tions of serum creatinine of gist as clinically appropriate	any grade, consider consulting with a	
Serum Creatinine)	function	(e.g. elevated serum BUN ar	may be related to changes in renal nd creatinine, decreased creatinine crease in urine output, proteinuria, etc.).	
		hould be thoroughly evaluate ease progression, infections	ted to rule out any alternative etiology etc.).	

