	If symptoms recur or worsen during corticosteroid tapering (<28 days of taper), increase the corticosteroid dose until stabilization or improvement of symptoms, then resume corticosteroid tapering at a			
		can be resumed at the next scheduled dose once event stabilizes to grade ≤1 or baseline and at least 5 days have passed after completion of steroid taper. Patients with endocrinopathies who may require prolonged or continued steroid	slower rate (≥ 28 days of taper) More potent immunosuppressives such as TNF inhibitors (e.g. infliximab) should be considered for events not responding to systemic steroids (also refer to the individual sections of the immune related adverse event for specific type of immunosuppressive).	

Table 4: Tox	Table 4: Toxicity Management Guidelines for Immune-related Adverse Events no Noted			
Adverse Event		Dose Modifications	Toxicity Guidance	
Event	Grade 3	 replacement can be retreated with study drug/study regimen on the following conditions: 1) The event stabilizes and is controlled 2) The patient is clinically stable as per treating physician's clinical judgment 3) Doses of prednisone are at less than or equal to 10mg/day or equivalent. Hold study drug/study regimen until resolution to ≤ Grade 1 or baseline. For Grade 3 and above asymptomatic amylase or lipase levels hold study drug/regimen. If complete work up shows no evidence of pancreatitis, may continue or resume study drug/regimen. Study drug/study regimen can be resumed at the next scheduled dose once event stabilizes to grade ≤ 1 or baseline and at least 5 days have passed after completion of steroid taper. 	Note: Discontinuation of study drug is not mandated for Grade 3 / Grade 4 inflammatory reactions attributed to local tumour response (e.g. inflammatory reaction at sites of metastatic disease, lymph nodes etc.). Continuation of study drug in this situation should be based upon a benefit/risk analysis for that patient made by the treating investigator.	
	Grade 4	Permanently discontinue study drug/study regimen. For Grade 3 and above		

Table 4: Toxicity Management Guidelines for Immune-related Adverse Events not Otherwise Noted			
Adverse Event	Dose Modifications	Toxicity Guidance	
	asymptomatic amylase or lipase levels hold study drug/regimen and if complete work up shows no evidence of pancreatitis, may continue or resume study drug/regimen.		

Table :	Table 5: Dosing Modification and Toxicity Management Guidelines for Infusion-Related Reactions			

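### Table 3 restarts Grade 3 hepatitis at the next scheduled dose with no steroid-taper condition, so an event that starts and resolves between two doses is re-dosed during its own taper of at least 28 days

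*Combined protocol and SAP*

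**What the plan says.** All of the following are in the combined protocol and SAP.

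- **Table 3, hepatitis, Grade 3, dose column (section 6.1).** For transaminases up to 8 x ULN or bilirubin up to 5 x ULN, treatment is held until Grade 1 or baseline. Then: "Resume study drug/study regimen administration at the next scheduled dose if elevations downgrade" to that level within 14 days. If they do not, treatment stops permanently. Higher elevations and Hy's law cases also stop permanently.
- **Same row, management column.** "Promptly initiate empiric IV methylprednisolone at 1 to 4 mg/kg/day or equivalent", and later "Once improving, gradually taper steroids over ≥28 days".
- **Table 3, hepatitis, Grade 2.** Treatment can resume at the next scheduled dose "once event stabilizes to grade ≤1 or baseline and at least 5 days have passed after completion of steroid taper". An earlier line in that cell reads "If improves to baseline then treat at next" scheduled date, which leaves open whether the wait applies after a return to baseline.
- **Table 4, other immune-related events, Grade 3.** Restart also requires that "at least 5 days have passed after completion of steroid taper".
- **Section 5.1.** "One cycle is defined as 28 consecutive days". Both drugs are given on day 1 of cycles 1 to 4, and durvalumab alone after that.
- **Section 5.5.2.** "Use of immunosuppressive medications for the management of investigational product-related AEs" is allowed, so the general steroid restriction does not block a dose.
- **Section 6.** The maximum hold is 56 days. The day from which it is counted is not stated.

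**The concern.** The row starts high-dose steroids for every Grade 3 event and asks for a taper at least as long as a cycle, yet ties the restart only to the liver tests. A site that follows it exactly gives the next dose while the patient is still on steroids. It is then not known whether the liver stays at Grade 1 without them, and the day-1 chemistry cannot show it because the blood is drawn on steroids.

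The restart condition is also looser than the one for the milder Grade 2 event and than the Table 4 condition for other Grade 3 immune-related events. Re-exposure is to both drugs in cycles 1 to 4. The Table 4 rule that stops treatment when a Grade 3 event recurs acts only after the patient has been re-dosed.

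**Working it through.** The plan gives no figure to reproduce, so this is a check of the calendar.

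**Inputs.** Cycle 28 days (section 5.1). Taper at least 28 days from first improvement, and resolution within 14 days of onset (Table 3, Grade 3 hepatitis). Post-taper wait 5 days (Grade 2 hepatitis; Table 4 Grade 3). Maximum hold 56 days (section 6).

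**Assumptions.** Last dose on day 1, later slots on days 29, 57 and 85. Onset on day d = 2 to 28. The taper starts on day i, one to 14 days after onset, and ends on day i + 28. Grade 1 or baseline is reached on day r, with i ≤ r ≤ d + 14.

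**General result.** If onset is after day 1, then i ≥ 2 and the taper ends on day i + 28 ≥ 30. That is after day 29, so any event resolved before day 29 is re-dosed inside its taper.

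**Example.** Onset day 8, improving day 11, Grade 1 by day 15. The taper ends on day 11 + 28 = 39. The day-29 dose falls with 39 − 29 = 10 days of taper left. With the 5-day wait the earliest date is day 44, so the dose moves to day 57.

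**Enumeration, current text.** The grid has 2,835 day combinations. These are scenarios, not probabilities.

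| Resolution | Combinations | Next dose inside taper |
|---|---|---|
| Before day 29 | 1,820 | 1,820 (2 to 27 days of taper left) |
| Day 29 or later | 1,015 | 560 |

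In the other 455 of the later group the taper has ended by the next dose.

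**Enumeration with the 5-day wait.** Restart is the first slot on or after day i + 33.
- Early-resolving courses: day 57 in 1,690 (i ≤ 24) and day 85 in 130 (i = 25 to 28).
- All 2,835: 28 days later than under the current text in 2,525, 56 days later in 190, unchanged in 120.

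**56-day maximum hold.**
- Counted from the first missed dose (day 29): a restart on day 85 is a hold of 85 − 29 = 56 days. No combination exceeds 56 with tapers of 28 to 38 days; 1 does with 39 days and 20 with 42.
- Counted from the last dose (day 1): a restart on day 85 is 84 days, so 980 of 2,835 exceed 56 even with a 28-day taper. None do under the current text.

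**Table 4 steroid limit** (10 mg prednisone or less within 56 days after the last dose, which is day 57). With a 28-day taper, all 1,820 early courses finish by day 28 + 28 = 56. With a 42-day taper, 910 of them are still tapering after day 57, but the rule applies only if the dose is then above 10 mg.

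**Number of patients.** Section 2.4.2 reports related Grade 3 or higher AST elevation in 4 of 102 NSCLC patients and ALT elevation in 3 of 102. For 40 patients: 40 × 4/102 = 1.6 if the ALT cases are among the AST cases, and 40 × 7/102 = 2.7 if all are different patients.

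**The case against.** **The gap may be deliberate.** Rows in Tables 3 and 4 that allow a restart tend to use either a post-taper wait or a resolution deadline with permanent discontinuation, not both. Grade 3 rash and Grade 3 neurotoxicity, and Grade 2 and 3 neuromotor syndromes, have a 30-day deadline and no wait. Grade 3 hepatitis has the shortest deadline and also excludes the worst cases. The pattern is real. It does not explain why an event that always gets high-dose steroids restarts more freely than Grade 2 hepatitis. A 14-day deadline shows only that enzymes fell on steroids.

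**Harm is not shown.** This stands. The documents give no evidence that dosing during a taper worsens outcome, and they accept 10 mg prednisone or less per day elsewhere (section 5.5.2, and endocrine restarts in Table 3). The steroid dose at re-dosing is unknown, because no taper schedule is given. The point is a missing safeguard, not a demonstrated injury.

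**Other safeguards exist.** Section 5.6 allows the investigator to stop treatment, chemistry is drawn on day 1 of each cycle, and recurrence of a Grade 3 related event ends treatment. These are discretionary, read on steroids, or act after re-dosing. None is a restart condition.

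**A reader might infer that every restarted Grade 3 hepatitis overlaps its taper, or that 1,820 of 2,835 is a risk.** Neither follows. Events that resolve on or after the next dosing day overlap only in some courses, and the combinations carry no weights.

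**A reader might also want one rule for all of Table 3.** The material does not support that. It would put a new condition on Grade 3 rash, neurotoxicity and neuromotor rows that are silent on the taper. With their 30-day deadline and the same method, 56 of 12,555 combinations (5-day wait) or 120 (7-day wait) pass the 56-day hold even when it is counted from the first missed dose.

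**Conclusion.** The point holds for the Grade 3 hepatitis row. With a 28-day cycle and a taper of at least 28 days, an event that starts after the dosing day and resolves before the next dose cannot have finished its taper when treatment restarts, and no other rule in the plan prevents that dose. The result needs only that steroids and the taper are given as written and that the next dose is given on its nominal day.

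The effect is small in numbers. The 1.6 to 2.7 of 40 is a ceiling in practice: it still includes Grade 4 events, transaminases above 8 x ULN, Hy's law cases and events that do not resolve within 14 days. It also comes from NSCLC at several dose levels, and section 2.4.2 notes more related events with tremelimumab above 1 mg/kg, while this trial gives about 1 mg/kg. The true number could be one or none. Severity is modest, but the change is worth making because it uses a clause the plan already contains.

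**What to change.** 1. **Table 3, Grade 3 hepatitis only.** Resume at the next scheduled dose once the event has reached Grade 1 or baseline within 14 days and at least 5 days have passed since the steroid taper was completed. Add that the 14-day limit applies to resolution, not to completion of the taper.
2. **Section 6.** State that the 56-day maximum hold is counted from the first missed scheduled dose. Without this, the added wait could force withdrawals.

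**Cost.** Two short text changes and no extra procedures. The affected patient usually restarts one cycle later and sometimes two. Tapers of about 39 days or longer can pass the 56-day hold in a few courses, and longer tapers may meet the Table 4 steroid limit if the dose is still above 10 mg prednisone. Other Table 3 rows stay as they are.

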	Grade 4	Permanently discontinue study drug/study regimen	treat Myasthenia Gravis. It should typically be administered in a monitored setting under supervision of a consulting neurologist.
			Patients unable to tolerate steroids may be candidates for treatment with plasmapheresis or IVIG.
			If Myasthenia Gravis-like neurotoxicity present, consider starting acetylcholine esterase (AChE) inhibitor therapy in addition to steroids. Such therapy, if successful, can also serve to reinforce the diagnosis.
			GUILLAIN-BARRE:
			Important to consider that the use of steroids as the primary treatment of Guillain-Barre is not typically considered effective. Patients requiring treatment should be started with IVIG and followed by plasmapheresis if not responsive to IVIG.

Table 4: Tox	Table 4: Toxicity Management Guidelines for Immune-related Adverse Events not Otherwise Noted			
Adverse Event	Dose Modifications		Toxicity Guidance	
Immune- related Adverse Events not Otherwise Noted	In addition to the above criteria for permanent discontinuation of study drug/regimen based on CTC grade/severity (Table 3), permanently discontinue study drug/study regimen for the following conditions:		Patients should be thoroughly evaluated to rule out any alternative etiology (e.g., disease progression, concomitant medications, infections, etc.).	
	 Inability to reduce corticosteroid to a dose of ≤10 mg of prednisone per day (or equivalent) within 56 days after last dose of study drug/regimen 		In the absence of a clear alternative etiology, all events should be considered potentially immune related.	
	ex rel	ecurrence of a previously perienced Grade 3 treatment- ated AE following sumption of dosing.	Symptomatic and topical therapy should be considered for low-grade events (Grade 1 or 2, unless otherwise specified).	
	Grade 1:	No dose delay.		
Grade 2:Hold study drug/study regimen dose until resolution to \leq Grade 1 or baseline.For persistent (greater low-grade (Grade 2) or (Grade \geq 3) events pri prednisone PO (or eq 2mg/kg/day or IV equivalence•If toxicity worsens then treat as Grade 3 or Grade 4If symptoms recur or corticosteroid taperin taper), increase the co dose until stabilization improvement of symptoms	 regimen dose until resolution to ≤ Grade 1 or baseline. If toxicity worsens then 	For persistent (greater than 5 days) low-grade (Grade 2) or severe (Grade ≥3) events promptly start prednisone PO (or equivalent) 1- 2mg/kg/day or IV equivalent.		

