7.9.2 Hepatic Function Abnormality

Adverse events of hepatic function abnormality of special interest to AstraZeneca/MedImmune are defined as any increase in ALT or AST to greater than $3 \times$ institutional ULN and concurrent increase in bilirubin to greater than $2 \times$ ULN (i.e., Hy's law cases). Concurrent findings are those that derive from a single blood draw or from separate blood draws taken within 8 days of each other. In the event of hepatic function abnormality where the etiology is unknown, timely follow-up investigations and inquiries should be initiated by the investigational site, based on medical judgment, to make an informed decision regarding the etiology of the event.

If the underlying diagnosis for the hepatic function abnormality is known (including progression of pre-existing disease such as metastatic malignancy), the diagnosis should be recorded as an AE/SAE.

If the underlying diagnosis for the hepatic function abnormality remains unknown, the term "hepatic function abnormal" should be used to report the AE/SAE. Hepatic function abnormality of unknown etiology, or which is considered attributable to investigational product, is required to be reported as "hepatic function abnormal" within 24 hours of knowledge of the event to the Overall PI and AstraZeneca/MedImmune representative(s) as an SAE (see Section 7.9). The investigator will review the data with AstraZeneca/MedImmune. The investigator should then use clinical judgment to establish the cause based on local standard of care and follow the subject by conducting testing as clinically indicated.

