Each reported event of hepatic function abnormality will be followed by the investigator and evaluated by AstraZeneca/MedImmune. If the etiology of the event remains unconfirmed and/or is considered related to investigational product, a prompt cumulative review of safety data and the circumstances of the event in question will be conducted and assessed by the MedImmune safety review committee (or equivalent) to determine whether continued dosing of current study subjects and/or study entry should be interrupted, whether the protocol will be modified, or whether the study will be discontinued permanently. Review and approval by the MedImmune safety review committee (or equivalent) is required for resumption of subject dosing or study entry in the event that the study is interrupted. Where applicable, regulatory authorities including IRBs/IECs will be notified of any actions taken with the study.

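### Table 3's Hy's law stop counts ALT only, unlike Section 7.9.2, so a Grade 3 AST-driven case with AST up to 8× and bilirubin up to 5× ULN that resolves within 14 days may resume dosing

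*Combined protocol and SAP*

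**What the plan says.** The hepatitis row of Table 3 is headed "Hepatitis (Elevated AST [SGOT], ALT [SGPT], and/or total bilirubin", so it covers both transaminases. For a Grade 3 event it gives four instructions:

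- With transaminases up to 8× ULN or bilirubin up to 5× ULN, hold treatment. "Resume study drug/study regimen administration at the next scheduled dose if elevations downgrade" to Grade 1 or baseline within 14 days.
- If they do not come down within 14 days, discontinue permanently.
- "For elevations in transaminases > 8" × ULN, or bilirubin above 5× ULN, discontinue.
- Discontinue permanently for any Hy's law case, defined as "ALT > 3x ULN + bilirubin > 2x ULN without initial findings of cholestasis" and no alternative cause. A regulatory guidance on drug-induced liver injury is cited for this criterion.

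Section 7.9.2, which governs immediate reporting, takes as its Hy's law cases "any increase in ALT or AST to greater than" 3× ULN with a concurrent bilirubin above 2× ULN. It does not exclude cholestasis or an alternative cause.

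**The concern.** The protocol gives one named liver signal two biochemical definitions, and the one that controls dosing omits AST. The row heading and the neighbouring 8× rule both cover AST, so the ALT-only line is the exception within its own row, and no reason is given.

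At stake is the safety of an individual patient. A patient whose injury shows mainly in AST could be re-exposed to both antibodies after a pattern that Section 7.9.2 calls Hy's law, while a patient with the same values in ALT could not.

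**Working it through.** This is a check of rule logic. The plan states no figure to reproduce.

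**1. Two mirror-image patients.** Both are Grade 3, have no cholestasis and no other cause, and are back to Grade 1 by day 10.

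| Rule | Patient A: ALT 6×, AST 2.5×, bilirubin 3× ULN | Patient B: AST 6×, ALT 2.5×, bilirubin 3× ULN |
|---|---|---|
| Transaminase > 8×? | 6 ≤ 8, no stop | 6 ≤ 8, no stop |
| Bilirubin > 5×? | 3 ≤ 5, no stop | 3 ≤ 5, no stop |
| Unresolved at 14 days? | day 10, no stop | day 10, no stop |
| Table 3 Hy's law (ALT > 3×, bilirubin > 2×)? | 6 > 3 and 3 > 2, **permanent stop** | 2.5 ≤ 3, not met |
| Outcome under Table 3 | stop | hold, then resume |
| Section 7.9.2 Hy's law case? | yes | yes (AST 6 > 3, bilirubin 3 > 2) |

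**2. Extent of the gap.** Fix ALT at 2.5× ULN and take every event as Grade 3 with no cholestasis and no other cause. Let AST be 4, 6, 7.9, 8, 8.1 or 12× ULN and bilirubin 2.5, 4, 5 or 5.1× ULN, each resolved or not resolved in 14 days. That makes 6 × 4 × 2 = 48 combinations, all of which meet the Section 7.9.2 definition.

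- 24 stop because AST is above 8× or bilirubin above 5×.
- 12 stop because they are unresolved at 14 days.
- 12 (AST 4 to 8×, bilirubin 2.5 to 5×, resolved) are held and then resumed.

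If Table 3 counted AST, those last 12 would stop. The 12 unresolved cases would stop at once instead of at day 14, and the other 24 would not change. The documents do not reproduce the CTCAE cut-offs, and the check does not need them, because the row has its own Grade 3 branch at or below 8× ULN.

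**3. Do other rules stop this patient before rechallenge?**

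- Section 6 caps a hold at 56 days. Recovery by day 14 plus at most 28 days to the next scheduled dose is 14 + 28 = 42 days from onset, below 56. The Grade 3 hepatitis row does not make resumption wait for the end of the steroid taper.
- Table 4 adds stops "In addition to the above criteria for permanent discontinuation of study drug/regimen based on CTC grade/severity (Table 3"). One is recurrence of a Grade 3 treatment-related event, which acts only after re-exposure. The other is failure to reduce steroids, which does not depend on the liver pattern.
- Section 5.6 allows removal for an unacceptable adverse event, which is a judgment.
- Section 5.2 bars tremelimumab retreatment after a Grade 3 event. That concerns retreatment after progression and does not prevent resumption of initial therapy.
- Section 7.9.2 requires reporting and review but does not automatically stop the patient.

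**4. How rare.** Section 2.4.2 reports treatment-related Grade 3 or higher AST increase in 4 of 102 patients on the combination (NSCLC, mixed doses). 4/102 = 3.9%, with an exact (Clopper-Pearson) 95% interval of 1.08% to 9.74%. Assuming the same rate in 40 patients, 40 × 4/102 = 1.57, with a range of 0.43 to 3.89. This is before requiring ALT at or below 3×, AST at or below 8×, bilirubin above 2× and up to 5×, no cholestasis, no other cause and recovery in 14 days, so for events graded 3 on AST the expected number is well below 1.6. The figure does not bound events graded 3 on bilirubin with lower-grade AST.

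**The case against.** A reader might infer that every Grade 3 AST-driven Hy's law case escapes a mandatory stop. The documents do not support that: the 8×/5× rule and the 14-day rule in the same row both cover AST. The gap exists only when all the listed limits hold together.

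A reader might also infer that ALT-only is a drafting slip. That cannot be shown. Table 3 cites a guidance for its criterion, and the same cell uses a general word for transaminases in one rule and ALT in another, which fits a deliberate choice as well as an omission.

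The strongest point against is that Section 7.9.2 is a reporting trigger, and a reporting trigger may properly be broader than a stopping rule. It already includes cholestatic and otherwise explained cases that Table 3 leaves out. This stands: the Section 7.9.2 label alone does not prove Table 3 wrong. It does not explain why two patients alike in every other respect are treated differently according to which transaminase rose.

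The safeguards are also real. With no alternative cause, this patient's event must be reported as an SAE within 24 hours. "The investigator will review the data with AstraZeneca/MedImmune". "If the etiology of the event remains unconfirmed and/or is considered related to investigational product", a prompt cumulative review must consider whether continued dosing should be interrupted, and dosing is on hold while the event lasts. All of this lowers the risk, but none of it mandates a stop, which is what Table 3 chose for the ALT case.

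Finally, the background counts do not show a patient in the gap. Related Grade 3 or higher AST increase occurred in 4 patients and ALT increase in 3, so at least 4 − 3 = 1 had the first without the second. That patient could still have had ALT above 3× ULN, and bilirubin is not given. The 102 patients also include tremelimumab doses up to 10 mg/kg, whereas 75 mg here is about 1 mg/kg, and Section 2.4.2 describes more treatment-related events above 1 mg/kg. The 1.6 may therefore be too high even as a starting figure.

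**Conclusion.** The point holds in its narrow form. As written, Table 3 lets dosing resume in a Grade 3 AST-driven case that satisfies every other part of its Hy's law criterion, provided AST is at most 8×, bilirubin at most 5× ULN and recovery comes within 14 days. The ALT mirror image must stop permanently.

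The conclusion about the rules follows from the text and needs no outside figure. The statement on rarity assumes that the NSCLC combination rate carries over to this trial. The patient at risk may never appear among 40, and the response-rate test is not touched. The change is still worth making, because the possible harm is re-exposure after serious liver injury and the remaining protections are discretionary or act too late. Confidence is moderate, mainly because intent cannot be established from the documents.

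**What to change.** In the Grade 3 hepatitis row of Table 3, change the criterion to *ALT or AST > 3x ULN + bilirubin > 2x ULN*, and keep the cholestasis and alternative-cause exclusions. The words *at any grade* may be added as an optional clarification. Section 7.9.2 needs no change. If ALT-only was intended, a sentence giving the reason would settle the matter instead.

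The cost is two words in one line. On rare occasions an additional patient would stop treatment permanently, a consequence the protocol already accepts for the equivalent ALT case.
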